The organization of the human visual system is an ideal model system suited for evaluation of the steerability of TI stimulation. The primary methodological advancement of TI is stimulation of deeper structures leaving superficial structures near the electrodes unaffected. The human primary visual system is organized "retinotopically", that is, with respect to the center of gaze. It is located within the calcarine sulcus, located in the occipital lobe at the posterior of the head. The most posterior part of the sulcus represents the center of gaze, and the most anterior part of the sulcus represents the periphery. Using this feature, we will examine if stimulation targeting the anterior calcarine sulcus induces a detectable visual change within the peripheral visual field, without impacting the center of gaze, located more superficially. Additional control sessions will evaluate the precision of TI steering.

Visual stimulation has historically been used as a preliminary investigation of non-invasive stimulation, in the study of transcranial magnetic stimulation (TMS) and transcranial electrical stimulation (tES). These sessions in healthy participants have shown acute effects of stimulation (e.g. brief phosphenes, transient scotomas) that are transient.

Clinical significance:

The importance of the problem we are tackling with TI stimulation is enormous, clinically speaking.

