Each subject will then undergo up to 4 TI stimulation sessions (2 minimum) separated by at least 2 days to minimize the risk of carry over effects of the stimulation. In each visit, the participant will receive TI stimulation to a region of retinotopic representation in the calcarine fissure. The cortical targets will be defined by electrical field modelling that will be used to optimize the electrode placement.

Stimulation visits will consist of TI stimulation combined with a visual discrimination task, with any changes in visual perception assessed by collecting behavioural responses (i.e. button presses) from the subject in response to visual stimuli presented before, during, and after TI stimulation.

Each visit will consist of up to four, 10 minute blocks of stimulation paired with a visual discrimination task. The stimulation blocks will be completed with TI stimulation at a difference frequency ranging from 1 to 80Hz, transcranial alternative current stimulation (tACS) stimulation with no temporal interference at a frequency ranging from 1 – 80HZ, or a no offset stimulation (e.g. matched carrier stimulation frequencies such that no envelope modulation is anticipated). The most common signal from visual cortex during wakeful relaxation is in the α frequency range (8-12 Hz). Due to this feature of visual cortex, we hypothesize that stimulation frequencies in and around α are likely to demonstrate TI efficacy. Moreover, since visual perception changes have been induced with tACS at 60Hz, we hypothesize that stimulation in and around this frequency will associate with detectable visual perception changes. We hypothesize that TI with a residual effective stimulation frequency of 1-80 Hz will be ideally suited for activation of the targeted visual cortex.

Each block will go as follows:

- 1. Baseline visual discrimination task to assess threshold
- 2. TI stimulation paired with the visual discrimination task and visual disturbance assessment (10 minutes)
- 3. Repeat visual discrimination task

Participants will have a 5 minute break between blocks.

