All participants will have a baseline visual field assessment with a computerized visual field device (a Humphrey field analyzer – HFA) to be completed in the BIDMC ophthalmology department. This assessment will also be completed at the end of each TI visit. The assessment consists of the participant being positioned against a forehead and chinrest while being asked to maintain fixation on a central target and while providing responses when a light stimulus is noted. One eye will be assessed at a time. The testing takes under 10 minutes. If an abnormality is noted at baseline, the study ophthalmologist will review the results and will share the findings with the patient in real-time and will recommend follow-up with their primary care provider and/or will recommend that they follow-up with a specialist provider in ophthalmology. They will be excluded from the study if an abnormality is discovered at baseline. If a change is noted at the end of a testing session, a study MD will evaluate the participant to determine the need for additional follow-up. If there are any immediate concerns, the participant will be further evaluated by the study ophthalmologist who will provide recommendations for observation or follow-up.

Visual Discrimination and Disruption Testing

Participants will be asked to perform a visual discrimination task within the targeted region of visual space and within a control region prior to, concurrently, and following TI stimulation.

Adaptive thresholds will be computed for orientation discrimination and contrast discrimination using an algorithmic approach. Discrimination thresholds for stimulated and unstimulated regions will be assessed using a within-subjects design using a repeated-measures ANOVA. Subjects will be asked to fixate at different locations on a screen and press a button, for example, to indicate where they see a visual stimulus.

TI Stimulation

TI stimulation will be generated by our prototype device and applied to the head via standard, carbon

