electrode pads. Similar to other forms of tES, TI will be delivered using a low amplitude (4mA or lower) electric current via a minimum of two and a maximum of 24 scalp electrodes. We will use computer simulations to optimize the location of the electrodes to maximize the amplitude of the envelope modulation in the targeted area (calcarine cortex subregions) while minimizing its amplitude in the neighboring or overlying cortex. Electrodes will be fitted with fiducial markers for post-processing localization of the electrodes in MRI. TI stimulation will be applied for up to 10 min (with 5-10s ramping-up and ramping-down periods) with a difference frequency of 1-80Hz.

As compared to modern tES, these values are reduced in duration, frequency and intensity relative to tES guidelines ("up to 60 minutes", frequencies up to 10kHZ), but follow overall guidance for rampingup and ramping down periods (Antal et al 2017, Clin Neurophysiology).

Control conditions will include non-TI controls (i.e. stimulation at a single frequency equal to the difference frequency of TI stimulation, thus no envelope of stimulation). TI delivered at the carrier frequency only, or TI with alternative difference frequencies expected to be suboptimal. The carrier frequency, as well as the current amplitude, will be selected according to the animal data, scaled according to the computer models, and governed by safety guidelines and considerations.

B. Statistical Considerations

a. **Sample Size Justification:** This study aims to assess the feasibility, focality, and steerability of TI stimulation in humans. Pilot testing with 9 healthy participants demonstrated the feasibility and safety of this study, and 9 participants were sufficient to identify a neurophysiological effect upon BOLD signal.

We aim to complete at least 12 subjects, but up to 20 will be entered to allow for attrition.

b. **Data Analysis:** This study has a primary aim of assessing visual discrimination thresholds before, during and after TI stimulation. These values will be entered into a repeated measures ANOVA to assess the impact of TI stimulation, with the primary outcome being an interaction between TIME factors (before, during and after TI) and visual field location (stimulated with TI vs unstimulated). All analysis will be conducted in either SPSS or R.

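### The only planned efficacy test, TIME x location, includes no TI-versus-control comparison, so a positive result would not by itself attribute the change to temporal interference

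*Combined protocol and SAP*

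**What the plan says.** **Analysis.** B3.B b takes discrimination thresholds before, during and after stimulation: "These values will be entered into a repeated measures ANOVA to assess the impact of TI stimulation". The paragraph then singles out one effect from that model, "with the primary outcome being an interaction between TIME factors (before, during and after TI) and visual field location (stimulated with TI vs unstimulated". B3.A (Visual Discrimination and Disruption Testing) describes the same ANOVA on stimulated and unstimulated regions. Subjects "perform a visual discrimination task within the targeted region of visual space and within a control region prior to, concurrently, and following TI stimulation", but the section does not say where the control region lies. The only other analysis text is the tabulation of safety events.

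**Controls.** B3.A (Temporal Interference (TI) Sessions) allows up to four 10-minute blocks per visit over two to four visits. A block may be TI, single-frequency tACS, "or a no offset stimulation (e.g. matched carrier stimulation frequencies such that no envelope modulation is anticipated". The block types are joined by *or*, with no number per condition and no order. B3.A (TI Stimulation) says "Control conditions will include non-TI controls", then adds carrier-only delivery or "TI with alternative difference frequencies expected to be suboptimal". B2 (TI Validation with Visual Field Stimulation) adds: "Additional control sessions will evaluate the precision of TI steering". None of these controls appears in the analysis text.

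**The concern.** The ANOVA is given the purpose of assessing the impact of TI, and what distinguishes TI is its low-frequency envelope. Comparing target with control region removes whatever changes in both, such as practice or fatigue. It does not remove a change that occurs only at the target but would also occur there without an envelope. A non-TI condition separates the two, and the sponsor's mouse work (B2, Animal studies) used one: matched 2 kHz currents evoked no movement, offset currents did. The human plan permits that control but gives it no part in the conclusion. Because no subject is assured a control block, the gap might not be repairable at analysis. At stake is whether a positive primary result may be reported as an effect of temporal interference or only as a location-specific change during TI.

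**Working it through.** **1. What each comparison estimates.** For one subject let D = (during minus before at the target) minus (during minus before at the control region). Changes common to both locations cancel. Write e for the envelope effect and c for any location-specific effect of carrier or current, assumed additive:

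- TI block: D = e + c
- matched no-offset block: D = c
- TI minus matched no-offset: e

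The during-versus-before part of TIME x location on TI blocks addresses e + c. It identifies e only if c = 0. Single-frequency tACS at the difference frequency does not fill this role, since B3.A itself says that tACS at 60 Hz has changed visual perception.

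**2. The plan's own figure.** B3.B a gives at least 12 completers from up to 20 entered, by precedent from a 9-subject pilot. It states no alpha, power, SD or effect size, so 12 cannot be reproduced. The attrition allowance implied is 1 - 12/20 = 40%.

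**3. Illustration.** Assume n = 12, two-sided 5%, effects in SDs of D, e = 0 and c of 0.3, 0.5 or 0.8 SD.

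- Noncentral t, 11 df, noncentrality c x sqrt(12): positive in 16%, 35%, 71% of trials.
- 2-df F(2,22), noncentrality 12 x 4c²/3 (change only during stimulation, sphericity): 16%, 37%, 77%.
- TI minus matched no-offset: 5% throughout, because c cancels.

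This shows what the planned test leaves open, not how likely it is.

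**4. Precision of the contrast, and carry-over.** With equal SDs and TI-control correlation r, the SD of the contrast is sqrt(2(1-r)). A one-sample t with n = 12 has 80% power at 0.889 SD, so the detectable contrast is 0.889 x sqrt(2(1-r)).

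For carry-over, suppose that TI always comes first and leaves a 0.5 SD location-specific after-effect in the next block's baseline, across the 5-minute break. A true null contrast then shifts by +0.5 SD if the after-effect decays during that block, or -0.5 SD if it doubles. The standardized shift is 0.5/sqrt(2(1-r)).

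| r | sqrt(2(1-r)) | Detectable contrast (SD) | Standardized shift | Null contrast significant |
|---|---|---|---|---|
| 0 | 1.414 | 1.26 | 0.354 | 20% |
| 0.3 | 1.183 | 1.05 | 0.423 | 27% |
| 0.5 | 1.000 | 0.89 | 0.500 | 35% |
| 0.7 | 0.775 | 0.69 | 0.645 | 53% |

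If both block types leave the same after-effect, counterbalancing makes the mean shift zero. If only TI leaves one, half the subjects are shifted by 0.5 SD and the mean shift is 0.5 x 0.5 = 0.25 SD, in either direction.

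**5. Unequal block numbers.** Average three TI blocks against one control block, with single-block correlation 0.3.

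- Variance of the TI average: (1 + 2 x 0.3)/3 = 0.533, SD 0.730.
- Variance of the contrast: 0.533 + 1 - 2 x 0.3 = 0.933, SD 0.966.
- Detectable contrast: 0.889 x 0.966/0.730 = 1.18 SD of the TI average.

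The equal-SD formula at the implied correlation 0.3/0.730 = 0.41 would give about 0.96. So the table applies only to equal numbers of blocks.

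**The case against.** **The location factor does more than remove shared change.** B2 predicts that targeting the anterior calcarine sulcus will alter the periphery and spare the more superficial centre of gaze. B3.A places electrodes to maximise the envelope at the target and minimise it in neighbouring or overlying cortex. B2 also says that conventional tES reaches depth only by stimulating overlying cortex more strongly. If the control region is the centre of gaze, current in general should act there at least as much, so a deep-only change is partial evidence for the envelope. This stands. A reader might infer that the planned test says nothing about TI, and that goes too far. It does not close the gap, because B3.A never defines the control region.

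**The rival explanation is hypothetical.** B2 calls the carriers too high to recruit effective firing, and the mice did not move under matched carriers. The remark on phosphenes in the Data Safety Monitoring Plan is not about kHz carriers. This also stands, and the rates in step 3 of the working carry no weight for severity. However, absence of movement in mice is not evidence on human visual thresholds, and the same plan calls TI minimally studied.

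**The study is early-phase, and its aims are safety, feasibility, focality and steerability.** TIME x location fits focality, so replacing it is not warranted. But B3.B b still names a primary outcome and an inferential test of the impact of TI. A reader might infer that the control data will go unused. The documents do not say so, and they do not exclude a condition factor; they specify neither.

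**Conclusion.** The point holds as a limit on attribution and should be fixed before the first TI session. The plan's one efficacy test can support a location-specific change during TI. It does not by itself exclude carrier or current as the cause, and no TI-versus-control analysis or guaranteed control block supplies the missing comparison. The stronger reading, that the primary result would be biased or the test invalid, is not supported: no document shows a location-specific carrier effect, and the test remains sound for focality.

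This conclusion is structural and rests on no effect size. The figures for the contrast and for carry-over rest on assumptions that the plan does not supply: n = 12, two-sided 5%, equal SDs, correlations from 0 to 0.7, and a 0.5 SD after-effect.

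**What to change.** Keep TIME x location on TI blocks as primary, and add to B3.A and B3.B b:

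1. **Allocation.** Every subject receives at least one no-offset block within the four-block limit, in counterbalanced order. It matches a TI block on target region, electrode montage, carrier and total current, so that only the frequency offset differs. The sponsor sets those values.
2. **Key secondary analysis.** The within-subject contrast TI minus matched no-offset on the location-specific during-minus-before change, as an estimate with 95% CI. Compare like with like: same target and same number of blocks per condition.
3. **Attribution rule.** Attribute an effect to temporal interference only if the primary test is positive and this CI excludes 0 in the same direction. The F test has no direction, so take it from the mean TI during-minus-before change. Otherwise report a location-specific change during TI, and do not read that as absence of a TI effect.

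A separate control visit is an alternative. The existing two-day gap would address carry-over across the short breaks, but target and montage must match there too, and the TI-control correlation may fall.

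**Cost.** Plan wording, one block of an already permitted type, and lower precision. An effect of 0.89 SD, which a TI-only contrast detects with 80% power, would be detected by the TI-minus-control contrast with about 51% power at r = 0 (0.89/1.414 = 0.63 SD) and 80% at r = 0.5. That is why a key secondary estimate is asked for rather than a co-primary test. Counterbalancing removes carry-over bias only if both block types leave similar after-effects.

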NCT Number:	NCT03747601
Official Title:	Temporal Interference Brain Stimulation (TI)
Document Type:	Protocol with Qualitative Analysis Plan
Document Date:	09/01/2020

PART B STUDY DESCRIPTION

	The Development and Human Translation of Temporal Interference Brain Stimulation
Principal Investigator	[name]

B1. PURPOSE OF PROTOCOL

The primary aim of this study is to translate temporal interference (TI) stimulation methodology into humans and examine its safety, feasibility, steerability, and focality. In the proposed early phase human experiment, we will assess the ability to apply TI stimulation along spatial dimensions to selectively modulate neural activity and assess the feasibility of selective targeting deep brain structures without exciting overlaying cortex. The overall goal of the study is to advance TI methodology and its translation to humans.

The specific aims in this study are to

- Assess the safety of TI stimulation.
- Assess the feasibility, focality, and steerability of TI stimulation by selectively modulating activity in subregions of a cortical area (calcarine cortex)

We hypothesize that TI stimulation can be used to impact different regions of the visual field that are represented within the calcarine fissure of the human brain.

We hypothesize that TI stimulation is possible in regions within the calcarine fissure without impacting intervening regions.

We hypothesize that TI will be well tolerated by human subjects and side effects will be consistent with other forms of transcranial electric current stimulation (tES).

B2. SIGNIFICANCE AND BACKGROUND FOR THE STUDY

Current brain stimulation methods have limitations:

[figure not shown]
Deep brain stimulation (DBS) has had great impact in disorders such as Parkinson's disease and obsessive-compulsive disorder and has potential for other disorders such as depression and Alzheimer's disease. DBS works by delivering focal electrical stimulation from electrodes surgically implanted in deep, often sub-cortical regions. Being a surgical procedure, it bears the potential for serious complications that limit adoption and scalability.

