Researchers at MIT have completed relevant pilot testing to assess whether TI stimulation is safe and can recruit activity in the human brain. We applied TI stimulation to the motor cortex of nine healthy volunteers (three females; mean age 27.5 ±5) and measured BOLD signals concurrently using fMRI. The experiment included four sessions consisting of six stimulation blocks - 10 Hz stimulation, 2 kHz stimulation, TI stimulation with 1:1 current ratio, TI stimulation with 1:3 current ratio, TI stimulation with 3:1 current ratio, and sham. Each stimulation block lasted 25 s with 5 s ramp-up and ramp-down periods. All participants tolerated the procedure without any adverse or side effects. No pain, tingling, cognitive changes, or sensory-motor difficulties were reported for the TI case by any of the participants. To test whether the TI stimulation changed the BOLD signal at the brain regions that were exposed to the electric fields we compared the T-score inside a spherical region of interest (ROI) in which activation was predicted by a subject-specific FEM modeling. We found that TI stimulation with a current ratio of 1:1 increased the BOLD signal at the center of the ROI. In contrast, TI stimulation with a current ratio of 1:3 increased the BOLD signal primarily at the frontal half of the spherical ROI, while TI stimulation with a current ratio of 3:1 increased the BOLD signal primarily at the frontal half of the spherical ROI, while TI stimulation with a current ratio of 3:1 increased the BOLD signal primarily at the frontal half of the spherical ROI, while TI stimulation with a current ratio of 3:1 increased the BOLD signal primarily at the frontal half of the spherical ROI, while TI stimulation with a current ratio of 3:1 increased the BOLD signal primarily at the frontal half of the spherical ROI, while TI stimulation with a current ratio of 3:1 increased the BOLD signal primarily at the frontal half of the spherical ROI, while TI stimulation with a current ratio of 3:1 increased the BOLD signal primarily at

TI Validation with Visual Field Stimulation:

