Safety information will be tabulated as frequency of expected events (e.g. headache), and non-conforming safety information will similarly be tabulated and reported.

C. Subject Selection

The population of the Greater Boston area is 84% Caucasian, 9% African-American, 5% Hispanic and 2% Asian, with relatively similar numbers of men and women. Participants of any gender, race, ethnicity, religion, and sexual orientation will be included. All efforts will be made to include equal numbers of both genders and to include minorities in the studies in equal proportions to the Boston area.

Inclusion Criteria:

- Normal healthy volunteer
- 18-45 years of age
- Normal or corrected-to-normal vision
- Right handed

Exclusion Criteria:

- Visual impairment that may interfere with eye tracking equipment (for example glasses with high reflection)
- Any current or past history of a psychiatric disorder
- Any current or past history of neurological disorders or acquired neurological disease (e.g. stroke, traumatic brain injury), including intracranial lesions
- History of head trauma resulting in prolonged loss of consciousness; or a history of >3 grade I concussions
- Current history of poorly controlled headaches including intractable or poorly controlled migraines
- Any systemic illness or unstable medical condition that may cause a medical emergency in case of a provoked seizure (cardiac malformation, cardiac dysrhythmia, asthma, etc.)
- History of fainting spells of unknown or undetermined etiology that might constitute seizures
- History of seizures, diagnosis of epilepsy, history of abnormal (epileptiform) EEG, or family history of treatment resistant epilepsy with the exception of a single seizure of benign etiology (e.g. febrile seizures) in the judgment of a board-certified neurologist
- Possible pregnancy. All female participants of child bearing age are required to have a pregnancy test
- Any metal in the brain, skull or elsewhere unless approved by the responsible MD
- Any medical devices (i.e. cardiac pacemaker, deep brain stimulator, medication infusion pump, cochlear implant, vagal nerve stimulator) unless otherwise approved by the responsible MD
- Substance abuse or dependence within the past six months
- Pregnancy; all female participants of child bearing age will be required to have a pregnancy test; any participant who is pregnant will not be enrolled in the study.

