Based on the experience with transcranial current stimulation, the following side effects (although unlikely) are possible:

- Sensations reported by subjects under the electrode: (These sensations can sometimes continue throughout and for a brief period following completion of the tES but usually resolve shortly after the initiation of tES)

- Mild tingling (20-70%)
- Light itching (30-40%)
- Slight burning (10-22%)
- Discomfort or mild pain (10-18%)

- Effects reported that occur only during tES:

• Visual sensation during switching on and off the stimulation (11%),

- Other effects that can occur both during and after tES include:

- Moderate fatigue (35%)
- Skin redness (30%)
- Headache (10-15%)
- Difficulties in concentration (11%)

- Additionally the following rare side effects have been described:

- Nausea (3%)
- Nervousness (<5%)
- Ringing in the ear (<1%)
- Changes in the activity of the prefrontal region have the potential to induce acute changes in mood. Hypomania has been reported in a few patients receiving tDCS for bipolar disorder (Loo et al., 2012) and depression (Arul-Anandam et al., 2010) but never in normal controls. Subjects with a history of a psychiatric disorder will be excluded from the study.
- Transient Visual Disturbance (2%)

- Although it has never been reported in tES, seizures are a theoretical risk.

Visual Discrimination and Periphery Testing:

Subjects may feel frustrated during the visual tasks. They will have breaks between the tasks to reduce the potential for frustration.

Confidentiality:

All data will be stored within secure BIDMC databases. The data will be stored without identifying information, with a code name assigned to the study participant. Data will be transferred with code names between BU and BIDMC via secure email and secure file transfer for MRI portion of the

experiment.

Risk/Benefit Ratio

The above stated risks are weighted with the potential application of non-invasive brain stimulation methods to impact brain function in healthy participants and various patient populations. Preliminary investigations as described here are necessary to validate the technique. We believe the balance of future application of brain stimulation exceeds the documented risks of transcranial electrical stimulation, and the protocol outlines procedures in place to mitigate potential risks of participation.

B6. RECRUITMENT AND CONSENT PROCEDURES

Recruitment

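### The safety aim rests on a frequency table without intervals in about 12 to 20 people, which cannot support a conclusion about side-effect rates

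*Combined protocol and SAP*

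**What the plan says.** B1 lists as a specific aim "Assess the safety of TI stimulation" and adds a hypothesis: "We hypothesize that TI will be well tolerated by human subjects and side effects will be consistent with other forms of transcranial electric current stimulation".

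The analysis that answers this aim is the single safety sentence in B3.B, b. Data Analysis: "Safety information will be tabulated as frequency of expected events (e.g. headache), and non-conforming safety information will similarly be tabulated and reported". It names no confidence interval, upper limit, denominator or counting unit (participant or session), and no way of setting the table against experience with tES.

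On size, B3.B, a. Sample Size Justification says: "We aim to complete at least 12 subjects, but up to 20 will be entered to allow for attrition". It gives no safety precision. For safety it relies on the pilot: "Pilot testing with 9 healthy participants demonstrated the feasibility and safety of this study". The pilot account in B2 reports: "All participants tolerated the procedure without any adverse or side effects".

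B5 lists 13 effects with percentages, introduced by: "Based on the experience with transcranial current stimulation, the following side effects (although unlikely) are possible". Examples are headache 10-15%, slight burning 10-22% and transient visual disturbance 2%. The list does not say whether these are rates per person or per session. Under B3.A each subject has two to four TI sessions.

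**The concern.** The hypothesis compares TI with other tES, and B5 supplies figures that a reader will naturally use for the comparison. Yet the planned output is counts and percentages alone. In a dozen people, a zero or a low count in such a table looks reassuring whether the true risk is negligible or substantial.

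The Sample Size Justification already treats nine event-free pilot participants as having demonstrated safety. If this trial's table is read the same way, an absence of visible excess could be carried into later studies as evidence that TI rates match those of tES. The protocol itself says TI has been little studied and that the goal is human translation, so the limits of the safety data should be visible in the report.

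**Working it through.** **The plan's own figure.** None exists to reproduce: no alpha, power, margin or detectable rate is stated for safety.

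**Inputs.** n = 12 (completion target) and n = 20 (maximum entered), from B3.B; pilot n = 9, from B2; listed rates from B5. Participants are the counting unit, which is an assumption. The number who receive any TI may lie between 12 and 20.

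**Step 1: upper limit when no event is seen.** Exact one-sided 95% limit = 1 − 0.05^(1/n). The two-sided 95% interval uses 0.025 in place of 0.05.

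| n | one-sided 95% | two-sided 95% |
|---|---|---|
| 12 | 1 − 0.779 = 22% | 1 − 0.735 = 26% |
| 20 | 1 − 0.861 = 14% | 1 − 0.832 = 17% |

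For the pilot's 0 of 9, the one-sided limit is 1 − 0.05^(1/9) = 28%.

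**Step 2: chance of never seeing an event with a true 5% risk.** At n = 12 this is 0.95^12 = 0.54.

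**Step 3: illustration, headache at n = 12 with a doubled risk.** The listed top rate is 15%, so the assumed true rate is 30%. The plan has no rule for calling a count consistent, so three assumed rules are compared.

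- *The exact 95% interval overlaps 10-15%.* Counts 0 to 4 pass: 4 of 12 has interval 9.9% to 65.1%, while 5 of 12 has lower limit 15.2%. P(X ≤ 4 | 12, 0.30) = 72%.
- *One-sided exact 5% test against 15%.* P(X ≥ 4) = 0.092 and P(X ≥ 5) = 0.024, so five events are needed to flag. The chance of passing is again 72%.
- *Observed rate not above 15%.* 12 × 0.15 = 1.8, so only 0 or 1 passes. P(X ≤ 1 | 12, 0.30) = 0.7^12 + 12 × 0.3 × 0.7^11 = 0.014 + 0.071 = 9%. With no true excess (15%), this rule would still flag 56% of the time.

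**Step 4: the same comparison over all 13 effects at n = 12, doubling the top listed rate.** Under the one-sided exact test, the doubled risk passes more often than not for 9 of 13 effects. The exceptions are itching (21%), fatigue (28%), redness (33%), and tingling, whose 70% cannot double. Under the observed-rate rule it does so for only 2 of 13: ringing in the ear (78%) and transient visual disturbance (61%).

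**Step 5: counting unit.** Suppose the 15% headache rate were per session and sessions were independent (both assumed). Incidence per participant with no true excess would then be 1 − 0.85² = 28% over two sessions and 1 − 0.85⁴ = 48% over four. A comparison that mixes units could create an apparent excess.

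**The case against.** Descriptive safety reporting is normal in a small early-phase study. The sample-size text names feasibility, focality and steerability, and the primary outcome is the ANOVA interaction. The hypothesis gives no rate and can be read as consistency in kind. The safety sentence fits that reading, because it separates expected from non-conforming events. The B5 percentages are risk disclosure and are not designated as analysis benchmarks. Around the table stand a tES questionnaire at each stimulation visit, end-of-visit perimetry, investigator review of events unexpected in nature, severity or frequency, and DSMB reports at least every six months.

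Most of this stands. It rules out treating the aim as a formal equivalence test, and it means a larger trial is not called for. The monitoring protects individual participants but sets no numerical bound on any rate, so it does not supply the missing precision. If only consistency in kind is meant, the report should say so.

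A reader might go further and infer that, as planned, a doubled risk of most listed effects would usually be declared consistent with tES. The documents do not support that. They contain no decision rule, and the answer swings with the rule assumed: 72% or 9% for headache, 9 or 2 of the 13 effects. Nor does any text say that TI will be reported as equally safe.

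**Conclusion.** The concern holds as a reporting gap. A frequency table in 12 to 20 people shows no uncertainty and cannot by itself support a claim about rates. The firm figures are the zero-event upper limits (one-sided 22% at 12 and 14% at 20) and the 54% chance of never seeing a 5% event in 12 people. They assume only that participants are the unit and respond independently. The doubled-risk figures illustrate how much depends on an unstated rule; they are not a property of the plan.

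A formal equivalence margin would not help at this size. If the margin were a doubling and the true rate equalled the listed one, the chance of meeting it at n = 12, using the exact one-sided 95% upper limit, is zero for every effect listed at 11% or less. The improvement is cheap and worth making, and it does not call the trial's design into question.

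**What to change.** In B3.B, b. Data Analysis, replace the safety sentence with a plan to:

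- report, for each expected and non-conforming event, the number and percentage of participants affected, among all who received any TI;
- attach an exact (Clopper-Pearson) 95% confidence interval to each percentage, including the upper limit when no events occur, and say whether that limit is one-sided or two-sided;
- show the B5 range alongside as descriptive context only, stating whether each rate is per participant or per session, or that the source does not say.

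Word the safety conclusion that answers the B1 hypothesis as descriptive, for example: no excess seen; rates up to the upper limit not excluded. Set no equivalence margin.

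The cost is a few sentences and some exact intervals, with no new data or participants. The downside is a more modest safety conclusion, since for most events sizeable rates will remain unexcluded.
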